6.4 Vaccine Administration and Sample Collection

A summary of vaccine administration will be prepared, describing the percent of subjects in the ITT population that received each vaccination, all vaccinations, and the time (days) between vaccination visits.

A summary table and listing will be prepared to describe the percent of TVP subjects providing evaluable (able to be evaluated via PCR for detection of poliovirus) stool samples for each planned collection day.

6.5 Safety Analyses

The TVP will be used for all safety summaries, with data summarized according to the vaccine received. Summaries will be presented by group and by time period, as well as across time periods within group and within vaccine group (e.g., combined Groups 1 & 2); for summaries presented by post-dose time period, these will be combined within Groups 1 & 2 (for each of UAM4 and UAM1) and within Groups 3 & 4 (UAM4) prior to dose 2. Summaries will also be presented according to candidate received, regardless of background vaccination status (i.e. combined Groups 1 and 2 from M1, combined Groups 1, 2, and 5 and combined Groups 3, 4, and 6) alongside the placebo group (Group 7). For summaries of adverse events in the post-dose-2 period, only subjects receiving the second vaccine will be included in summaries.

For all safety summaries and listings, any subject receiving a non-study vaccination will have safety data following receipt of the non-study vaccine removed from TV population analyses. For each safety category (AEs, safety labs, vital signs and physical exam findings), separate listings will be created for safety data from TV population members following receipt of non-study vaccine. If any listing contains data from more than 5 subjects, a table will be created to summarize the data.

Only adverse events collected on or after the date of first vaccination will be included in summaries; all AEs, regardless of collection time point will be included in listings.

The original terms used in the designated sections of the eCRFs by Investigators to identify AEs will be fully described and coded according to the Medical Dictionary for Regulatory Activities (MedDRA), including System Organ Class (SOC) and Preferred Term (PT). The following categories will be used by the Investigator to describe the causality assessment:

Unrelated – there is not a reasonable possibility that the study vaccine caused the AE.

Unlikely – suggests that only a remote connection exists between the study vaccine and the event. Other conditions, including concurrent illness, progression or expression of the disease state or reaction to concomitant medication, appear to explain the AE.

Possible – suggests that the association of the AE with the study vaccine is unknown, however the event is not reasonably supported by other conditions.

Probable – suggests that a reasonable temporal sequence of the AE with vaccine administration exists and, in the Investigator's clinical judgment, it is likely that a causal relationship exists between the vaccine administration and the AE, and other conditions (concurrent illness, progression or expression of the disease state, or concomitant medication reactions) do not appear to explain the AE.

Throughout, when the word “related” is used to refer to adverse events, it is to be understood to refer to those events considered either possible or probable.

All AEs will be summarized by type, seriousness, severity, causality, by group and overall. AEs will be summarized with tables at the subject level, where a subject contributes to the total once under the maximum severity/relationship of the event type. An adverse event summary table will be prepared summarizing the number of subjects with any unsolicited AE (and by maximum severity and by maximum relationship), any SAE by type and by maximum relationship, any related SAE, any severe unsolicited AE by maximum relationship, any serious or severe AE, any AEs leading to study/treatment withdrawal, any grade ≥ 2 unsolicited AE, and any solicited AEs by maximum severity. All adverse events will be presented in a listing, and separate summaries and listings will be developed for AE categories of special interest, as described below.

All summaries of unsolicited adverse events will present the number and percentage with a qualifying event, including a two-sided 95% exact confidence interval for the proportion, as well as the total number of qualifying events. Summaries of solicited adverse events will be summarized similarly but will omit the total event count.

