Solicited systemic AEs (Diary) ^k	X-----X				
Remote contact for safety follow-up ^m					
Concomitant therapies ⁿ	X	X	X	X	X
Adverse events ⁿ	X	X	X	X	X
Reminder Code of Conduct ^o	X	X	X	X	X

a. In case of early termination the subjects will be asked to return to the clinical site within 14 days after discontinuation for assessments as outlined on Day 28.

b. No study-related assessment is to be carried out before signing of the informed consent form.

c. Including polio vaccination history.

d. Includes weight and height at Day 0. After Day 0, symptom-directed physical examination.

e. Prior to vaccination.

f. Blood pressure and heart rate (supine) and oral body temperature. On Day 0, vital signs will be assessed prior to and 30 min after vaccination.

g. For a list of assessments, please see Appendix 1: Overview of Laboratory assessments.

h. In women of childbearing potential, a urine pregnancy test will be performed.

i. Includes HBsAg, anti-HCV and anti-HIV antibodies and IgA.

- j. The subjects will be kept under medical supervision for at least 30 min after vaccination.
- k. Solicited AEs will be collected for Days 0-7.
- l. Subjects will be asked to collect the first stool of every day in the provided container and to store this in the provided thermal bag with cooling elements: daily collection on Days 0 to 10 plus collection on Days 14, 21, V4 minus 1 or 2 days and V5 minus 1 or 2 days. At Day 0, the storage procedure will be explained and the collection material provided. Subjects who are still shedding virus in one of the 3 last stool samples will be asked to collect 3 consecutive stool samples every 3 weeks till end of shedding.
- m. Remote contact (text message by sms, WhatsApp or email) on day 3 and on Day 21 for safety follow up and reminder stool collection scheme .
- n. Adverse events and intake of concomitant medication(s) will be monitored continuously from informed consent until the last study-related activity. The subjects can record unsolicited AEs on their diary card.
- o. After signing on screening visit, weekly reminder Code of Conduct by email or sms and on each visit to emphasize the need and importance of hygienic measures and respecting the inclusion/exclusion criteria until end of study.

TIME AND EVENTS SCHEDULE – GROUPS 2, 4, 5, 6 AND 7

Assessments	1	2	3	4	5	6	7	8
Visit	1	2	3	4	5	6	7	8
Time of Visit (days)	D0	D7 (+/- 2D)	D14 (+/- 3D)	D28 (+/- 2D)	D35 (+/- 2D)	D42 (+/- 3D)	D56 ^a (+/- 2D)	D 70 (+/- 4D)
Visit window								

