8. ASSESSMENTS

8.1 TIMING OF ASSESSMENTS

An overview of the timing of treatment(s) and assessments is given in the Time and Events Schedules below.

Subjects will be given a full explanation of the nature of the study and written informed consent (approved by the local ethics committee) will be obtained according to local requirements before any study-related assessment will be carried out.

The Code of conduct contains an overview of in-/exclusion criteria and hygienic measures to be taken by the subject during the study. Subjects will be explained the content of this document and asked for their agreement during screening. They will receive a copy as a memory aid at home. At each visit and weekly by email or sms subjects will be reminded of the content of this document.

Adverse events and the intake of concomitant medication will be monitored continuously from informed consent until the last study-related activity.

After the predose procedures, (signing of Informed consent and Code of Conduct, reviewing of in-/exclusion criteria, medical history, medication history, demographic data, performing physical examination, pregnancy test, assessing vital signs and blood sample cfr. Time and Events Schedule), the subjects will receive the first dose of study vaccine according to the procedure described in Section 6.7, followed by further assessments as outlined in the Time and Events schedule.

The subjects will be kept under medical supervision for at least 30 min after each vaccination.

Thermometers and a diary card will be distributed to subjects and the use of the diary card will be explained.

Unscheduled visits can be planned for instance:

- to obtain additional information to ensure safety to the subject. Additional blood and urine samples for clinical assessment may be taken at the discretion of the Investigator.

Findings made during unscheduled visits should be reported in the source documents and in the designated sections of the eCRF.

TIME AND EVENTS SCHEDULE – GROUPS 1 AND 3

Assessments	1	2	3	4	5
Visit					
Time of Visit (days)	D0	D7 (+/- 2D)	D14 (+/- 3D)	D28 ^a (+/- 2D)	D 42 (+/- 4D)
Visit window					
Informed consent ^b	X				
In-/exclusion criteria	X				
Medical history/concomitant diseases	X				
Medication history ^c	X				
Demographic data	X				
Physical examination ^d	X ^e	X	X	X	X
Vital signs ^f	X ^{e,f}	X	X	X	X
Clinical laboratory tests ^g	X ^e	X	X	X	
Pregnancy test ^h	X ^e				X
Serology ⁱ	X ^e				
Randomization	X				

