8.3 SAFETY EVALUATIONS

The safety assessment in this study will be based on AEs, clinical laboratory tests, vital signs, and physical examination, as described in the following sections.

8.3.1 *Adverse Events*

Adverse events will be monitored continuously from informed consent until the last study-related activity. At regular intervals during the study, subjects will be asked non-leading questions to determine the occurrence of any AEs. All AEs reported spontaneously during the course of the study will be recorded as well.

For detailed definitions and reporting procedures of AEs, see Section 11.

Solicited AEs will be recorded for 7 days following each vaccine dose using a Diary Card.

8.3.2 *Clinical Laboratory Tests*

Blood samples of about 15 mL will be collected at the time points indicated in the Time and Events schedule.

Biochemistry and hematology testing will be performed on these samples, as well as serology testing (HBsAg, anti-HCV, anti-HIV antibodies, and total serum IgA) on the sample from Day 0. In female subjects of childbearing potential, also urine β -human chorionic gonadotropin (hCG) will be tested at Day 0 and at last visit in each group and at Day 28 in Groups 2, 4, 5, 6 and 7.

Standard laboratory tests as outlined in Appendix 1 will be performed by the local laboratory.

The Investigator must review the laboratory report, document this review, and record any change occurring during the study he/she considers to be clinically relevant in the source documents and in the AE section of the eCRF. Laboratory values outside the normal range will be flagged and their clinical relevance and causality will be assessed by the Investigator. A copy of all laboratory reports must be filed in the subject's medical records.

Samples that remain after protocol-specific assessments have been performed may be used for further exploratory work on polio. No human DNA or RNA analysis will be performed.

8.3.3 *Vital Signs*

Vital sign parameters will be assessed after 5 minutes in supine position at the time points indicated in the Time and Events schedule.

The vital sign parameters that will be assessed are supine systolic and diastolic blood pressure (SBP and DBP, respectively), pulse rate and oral body temperature.

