11. ADVERSE EVENT REPORTING

11.1 DEFINITIONS

Adverse Event

An AE is any untoward medical occurrence in a clinical study subject administered a medicinal (investigational or non-investigational) product. An AE does not necessarily have a causal relationship with the treatment. An AE can therefore be any unfavorable and unintended sign (including an abnormal finding), symptom, or disease temporally associated with the use of a medicinal (investigational or non-investigational) product, whether or not related to that medicinal (investigational or non-investigational) product.

This includes any occurrence that is new in onset or aggravated in severity or frequency from the baseline condition, or abnormal results of diagnostic procedures, including clinical laboratory test abnormalities.

Serious Adverse Event

An SAE is any untoward medical occurrence that at any dose meets any of the following conditions:

- results in death;
- is life-threatening, i.e., the subject was at risk of death at the time of the event (e.g., ventricular fibrillation and anaphylaxis). The term does not refer to an event which hypothetically might have caused death if it were more severe.
- requires inpatient hospitalization or prolongation of existing inpatient hospitalization:
Hospitalization refers to an overnight admission into hospital for the purpose of investigating and/or treating the AE. Hospitalization for an elective procedure, or routinely scheduled treatment for a pre-existing condition that has not worsened, is not an SAE.
- results in persistent or significant disability/incapacity, i.e., causing substantial disruption of the subject's ability to conduct normal life;
- is a congenital anomaly/birth defect;
- is medically important: Medical or scientific judgement should be exercised in deciding whether reporting is appropriate in other situations such as important medical events (IMEs) that may not be immediately life threatening or result in death or hospitalization but may jeopardize the subject or may require medical or surgical intervention to prevent one of the other outcomes listed in the above definition. Examples of such events are intensive treatment in an emergency room or at home for allergic bronchospasm, blood dyscrasias, or convulsions that do not result in hospitalization or development of drug dependency or drug abuse.

Solicited Adverse event

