11.2 INTENSITY OF ADVERSE EVENTS

Severity of solicited AEs will be scored as indicated on the Diary Card.

Each unsolicited AE must be rated on a 3-point scale of increasing intensity as outlined below:

Grade 1:

Mild; an AE that is easily tolerated by the subject, causing minimal discomfort and not interfering with everyday activities.

Grade 2:

Moderate; an AE that is sufficiently discomforting to interfere with normal everyday activities.

Grade 3:

Severe; an AE that prevents normal everyday activities. Such an AE would, for example, prevent attendance at work and would necessitate the administration of corrective therapy.

Fever will be assessed using the NIH CTCAE grading scale:

Grade 1: 37.5°C to 38.0°C

Grade 2: 38.1°C to 39.0°C

Grade 3: >39.0°C

Lab results will be assessed using the NIH CTCAE version 4.03 (toxicity grades). For grade 1 values the investigator will use his clinical judgement to determine these values as clinically significant. Lab values above grade 1 will automatically be deemed clinically significant, and recorded as adverse events.

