6.5.1 Primary Safety Endpoints

- Solicited adverse events:
 - Serious/severe solicited adverse events will be summarized by group, by post-vaccination time period as well as overall (under maximum severity), and by term by post-vaccination time period as well as overall (under maximum severity), as well as listed.
- Unsolicited adverse events:
 - Serious/severe unsolicited AEs will be summarized by group, maximum causality and by class (serious vs severe) under maximum causality, by post-vaccination

time period (prior to dose 2 vs following dose 2) as well as overall, and reasons for SAE classification (wherever such subcategories are relevant), as well as by SOC and PT among serious events only (and among those serious and related), and among severe events only (and among those severe and related). These events will also be listed.

- Listings will be prepared for those subjects who died or withdrew from the study due to an AE.

Two-sided p-values from the Fisher exact test of the number of subjects with an event will be presented for:

- Severe solicited events (overall, and by event term)
- Any serious unsolicited event
- Any serious and related unsolicited event
- Any severe unsolicited event
- Any severe and related unsolicited event

These comparisons will be conducted for the following groups:

- UAM4 Groups 1 & 2 vs UAM1 Groups 1 & 2
 - Post-dose-1 and overall, TVP
- UAM4 Group 2 vs UAM1 Group 2
 - Post-dose-2, TVP subjects who received both doses
- UAM4 Groups 3 & 4 vs UAM1 Groups 1 & 2
 - Post-dose-1 and overall, TVP
- UAM4 Group 4 vs UAM1 Group 2
 - Post-dose-2, TVP subjects who received both doses
- UAM4 Group 5 vs UAM4 Group 7
 - Post-dose-1, post-dose-2, and overall, TVP
- UAM4 Group 6 vs UAM4 Group 7
 - Post-dose-1, post-dose-2, and overall, TVP

Comparisons for both solicited and unsolicited events will be conducted separately for post-dose-1 and post-dose 2, as well as following any dose. Comparisons involving post-dose-2 data will include only subjects receiving both doses.

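### The SAP's date-based filter lets a severe abnormality in the pre-dose Day 0 sample count as a post-vaccination event in the primary safety summaries and tests

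*SAP*

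**What the plan says.** SAP 6.5 decides which AEs enter the safety tables: "Only adverse events collected on or after the date of first vaccination will be included in summaries". All other AEs go to listings only. The rule uses a calendar date and the time of collection. It mentions neither onset nor clock time. SAP 5.1 likewise defines baseline as a day.

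Protocol 8.3.1 starts AE recording before any dose: "Adverse events will be monitored continuously from informed consent until the last study-related activity". Protocol 8.1 puts consent, examination, vital signs and the blood draw ahead of the first dose at the same visit: "assessing vital signs and blood sample cfr. Time and Events Schedule), the subjects will receive the first dose of study vaccine". The Time and Events Schedules place all of these on Day 0 and footnote the Day 0 laboratory sample as taken before vaccination.

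On laboratory results, Protocol 11.2 states: "Lab values above grade 1 will automatically be deemed clinically significant, and recorded as adverse events". It makes no exception for the Day 0 sample.

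The primary safety endpoint is SAEs and severe AEs. SAP 6.5.1 tabulates the serious and severe unsolicited AEs by "time period (prior to dose 2 vs following dose 2) as well as overall", and gives two-sided Fisher p-values for, among others, subjects with any severe unsolicited event. The comparisons are labelled post-dose-1, post-dose-2 and overall.

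**The concern.** An event found before the dose cannot be a vaccine effect, yet the stated filter lets it into the primary safety count. The periods in SAP 6.5.1 include none before dose 1, so such an event has only two places to go: the period before dose 2, and the overall count.

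The kind of event matters here. Protocol 1.3.1 reports that severe unsolicited AEs in the first-in-human study were mostly asymptomatic laboratory abnormalities, and that half the participants had severe CK elevations. Liver and muscle enzymes are not eligibility criteria, so a subject with a severe CK value at Day 0 can be enrolled and dosed.

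Two consequences follow. In the randomised IPV comparison, pre-dose events should occur about equally in the arms, so counting them dilutes a real difference. In the OPV comparison with UAM1, they could also bias the result if recording practice or the measured parameters differed between the studies. Protocol 10.1.4 promises laboratory comparison with UAM1 only where possible and names ALT and AST as examples.

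**Working it through.** **Step 1: the texts side by side.**
- Start of AE recording: consent, on Day 0 before the dose (Protocol 8.1, 8.3.1).
- Pre-dose sample: Day 0 (both schedules).
- Filter: date of first vaccination, which is Day 0 (SAP 6.5).

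Any AE recorded from consent onwards is thus dated Day 0 or later and passes the filter. Because the rule refers to collection, an event that began before the dose but was reported later also passes.

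**Step 2: what reaches the primary endpoint.** A pre-dose value above grade 1 becomes an AE under Protocol 11.2. Only a severe or serious one enters the primary endpoint; a moderate one enters only the secondary AE summaries. Of the Fisher tests, those on solicited events rest on post-vaccination diaries and are barely touched. An SAE between consent and dose is improbable, and an investigator should not judge a pre-dose finding related. The exposure is therefore mainly the test of any severe unsolicited event, post-dose-1 and overall.

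**Step 3: illustration of size.** The plan states no figure for this point. I borrow 6% and 4 × 6% = 24% from Protocol 10.2. Those are rates of laboratory elevation of unstated grade, not severe-AE rates. The sample size built on them reproduces closely: exact power of the one-sided 5% score test at 44 per group is 79.7% against the stated 80%, and the unpooled formula gives (0.06×0.94 + 0.24×0.76) × (1.645 + 0.842)² / 0.18² ≈ 45.6. Nothing in that calculation is contested.

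Let b be the share of subjects with a severe pre-dose finding, assumed to be 0% to 10% and independent of post-dose events. The counted rate is 1 − (1 − b)(1 − p), so the risk difference shrinks by the factor (1 − b). Fisher power (two-sided, 5%) is by full enumeration:

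| b, both arms | Counted rates | Risk difference | Power, 16 per group | Power, 44 per group | Power, 100 per group |
|---|---|---|---|---|---|
| 0% | 6.0% vs 24.0% | 18.0 points | 15% | 58% | 95% |
| 2% | 7.9% vs 25.5% | 17.6 points | 14% | 51% | 91% |
| 5% | 10.7% vs 27.8% | 17.1 points | 12% | 43% | 84% |
| 10% | 15.4% vs 31.6% | 16.2 points | 10% | 34% | 73% |

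Sixteen and 44 are the minimum and full IPV group sizes; 100 is one candidate's combined OPV groups, set against 100 in UAM1.

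**Step 4: unequal counting against UAM1.** Suppose the true post-dose rate is 6% in both studies, with 100 subjects each, and pre-dose findings are counted only on the UAM4 side (an assumption, for instance a parameter not measured in UAM1). The Fisher rejection rate rises from 2.4% at b = 0 to 4.7%, 16% and 50% at b = 2%, 5% and 10%.

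**The case against.** The best defence is that SAP 6.5 sets a necessary condition for inclusion and does not call pre-dose events post-vaccination. SAP 6.5.1 labels its comparisons post-dose-1, post-dose-2 and following any dose, and it describes the unsolicited periods as post-vaccination. A pre-dose event follows no dose. SAP 6.2 treats baseline laboratory deviations as baseline characteristics, and Protocol 8.3.2 asks the investigator to record changes during the study. Protocol 11.1 speaks of occurrences "new in onset or aggravated in severity or frequency from the baseline condition, or abnormal results of diagnostic procedures".

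This shows that the intention was probably to exclude such events. It does not settle the matter. The last clause of that definition admits an abnormal result in its own right, Protocol 11.2 is automatic, and none of these texts overrides the explicit filter. Two programmers could build different primary tables from the same plan.

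The defence is right on three stronger readings that a reader might infer:
- **That the problem recurs at Day 28.** It does not follow. SAP 6.5.1 splits at dose 2 and not by date, the date rule concerns the first vaccination only, and the schedule marks the Day 28 bloods as pre-dose. On that text they fall before dose 2.
- **That the enzyme question from Phase 1 is compromised.** SAP 6.5.2 gives ALT, AST, CK, GGT, bilirubin and albumin their own analysis, limited to post-baseline values, with shift tables against baseline.
- **That a known amount of power is lost.** The rates are assumed, Protocol 10.1.4 describes the safety analysis as descriptive, and no sample size or stated decision depends on these Fisher tests.

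**Conclusion.** The point holds in a limited form. As written, SAP 6.5 allows a severe pre-dose Day 0 abnormality into the primary summaries and Fisher tests of any severe unsolicited event. This is in conflict with the post-dose wording of SAP 6.5.1 and out of step with the post-baseline limit of SAP 6.5.2. It does not mean that every abnormal pre-dose blood result reaches the primary endpoint, and the post-dose-2 tests are not affected.

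The expected effect is dilution in the randomised IPV comparison, with possible bias in either direction against UAM1. The size cannot be stated, because the documents give no rate of severe pre-dose findings; the figures above only show sensitivity under assumed rates. The conclusion also rests on abnormal Day 0 results being recorded as AEs, which Protocol 11.2 requires but other wording leaves open. It deserves correction before database lock, but it does not undermine the safety analysis as a whole.

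**What to change.** In SAP 6.5, replace the date rule with these:
- AE summaries and the SAP 6.5.1 tests include only AEs with onset after administration of the first dose.
- AEs derived from the pre-dose Day 0 blood sample, vital signs or examination are baseline findings. They are listed, but not summarised or tested unless they worsen in grade after dosing.
- A Day 0 symptom whose onset cannot be placed before the dose counts as post-dose. This default is needed because the AE listing in SAP 6.5.2 carries dates and onset day, with no mention of clock time.
- The same rule applies to UAM1.

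The cost is a few sentences. For laboratory and examination findings no new data are needed, since the schedule already marks these assessments as pre-dose. The downside is slightly fewer counted events.
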